### **3.5 STUDY MONITORING PLAN**

#### **3.5.1 Reporting Serious Adverse Events**

Serious Adverse events (SAEs) will be monitored continuously using a special form that will be required for any event that meets the following criteria:

- Results in death;
- Is life-threatening;
- Requires hospitalization or prolongs existing hospitalization;
- Results in persistent or significant disability or incapacity;
- Any other serious or unexpected adverse event that the study investigator(s) feels should be reported.

The specific adverse events to be monitored in this trial include maternal death, upper GI bleeding (vomiting blood), fetal anomaly, gastroschisis, post-partum hemorrhage, or antepartum hemorrhage. The occurrence of any of these events will also trigger completion of the Serious Adverse Events Form.

### **3.5.2 Method and Timing for Reporting Serious Adverse Events**

The Senior Foreign Investigator (SFI) must report the following SAEs by emailing or faxing a copy of the form to RTI as follows:

Within 48 hours of SFI's notification of the event:

- All maternal deaths
- All SAEs with a definite or suspected/probable relationship to the intervention

Within 7 days of SFI's notification of the event:

- All life-threatening events
- All SAEs considered to have a probable or possible relationship to the intervention.

All emailed or faxed forms should also be entered into the DMS and transmitted within 7 days as a back-up to ensure no SAE is missed. Additional reporting procedures include:

- RTI will forward all SAEs to the US-based Principal Investigator (PI) and NIH for further assessment of relationship to study intervention.
- The PI and SFI will be responsible for reporting to their respective IRB and other regulatory authorities per their institutional policy.
- RTI will be responsible for reporting SAEs to the DMC bi-annually at a minimum. The frequency of reporting to the DMC may be increased if the reported events or interim data reviews by the DMC indicate that more frequent safety monitoring is needed.

Any SAE considered unrelated to the intervention is not required to be reported in an expedited manner. These events should be entered into the data management system and transmitted per routine procedures.

### **3.5.3 Data Monitoring Plan and Stopping Rules**

All the Global Network sites will report data to the Global Network Data Coordinating Center, located at RTI International. The data will be used to evaluate protocol adherence and site performance (e.g., recruitment, loss to follow-up, data quality). The DCC will provide standardized progress reports to NICHD and the site investigators on a monthly basis to monitor outcome variables and adverse events.

Oversight of the trial will be handled by two principal groups with different focuses:

- 1) **Protocol-focused Steering Committee (SC):** The SC is comprised of the Central Study Team from Christiana Care and Jawaharlal Nehru Medical College (JNMC), NICHD, the DCC, and investigators from each of the participating sites (see **Appendix 5**). The Central Study Team, with assistance from NICHD and the DCC, will have primary responsibility for overall study design, development of study materials and procedures, and oversight of study implementation. They will meet via conference call bi-weekly to monitor study progress and ensure proper implementation of the trial. The Site Investigators will be responsible for providing guidance on study design, developing site-specific implementation plans, ensuring study staff are properly trained, and providing oversight of the

study at the site level. The SC will convene via conference call at least once per quarter and will meet in person twice a year to discuss study design and implementation issues. Members of the Central Study team, NICHD, and RTI will also conduct site visits, as the budget allows, to bolster enthusiasm, provide hands-on training and education to the participating staff, and address site-specific issues, if any.

2) **Data Monitoring Committee (DMC)**: The DMC, a standing group that monitors all NICHD-funded Global Network studies, will be responsible for ensuring safe and ethical treatment of study participants through monitoring of the study. The membership will include, at a minimum, a statistician, obstetrician, pediatrician and an expert in international health. The DMC designated by NICHD will review the data collected at approximate 6 month intervals throughout the course of the study. The DMC reports, which are prepared by the Data coordinating center, will include information on study enrollment rates and participant progress through the study, participant compliance with protocol-specified treatment regimens, protocol violations, adverse events, and efficacy outcomes. The focus of the DMC review will be on monitoring participant safety and study progress/futility but data on treatment effectiveness will also be presented to frame the DMC discussions on safety and futility. However, no formal interim analysis of efficacy or effectiveness are planned and the DMC will not be responsible for stopping the trial for efficacy. The DMC will be charged with monitoring adverse events and side effects from LDA. All known associated side effects and specific obstetric or fetal concerns will be considered reportable to the DMC. The study will be reviewed by the DMC bi-annually at a minimum, but may be reviewed more frequently if concerns are raised about participant safety or about adequate process of the study.

### **3.6 DATA MANAGEMENT PROCEDURES**

Data will be collected both prospectively and from existing clinical records, using hard copy forms or Android Tablets. Regardless of data capture methodology, all data will be kept confidential. Each participant will be assigned a unique study ID which will be used to identify the participant. Only the screening log will contain the name (which is not transmitted). If hard copy forms are used, they will be retained in a secure location for possible editing or queries at the central data entry site. Data will be entered into computers using the Data Management System (DMS) developed by RTI and the assigned study number. The DMS will also allow site staff to produce project reports and backup the study database. Electronic data will be transferred from each data management computer to a single Research Unit Data Center (RUDC) in each country, creating a complete data repository. At least once a week, data will be transmitted from the RUDC to the DCC at RTI. The data center will conduct training on the DMS system, as needed, and will maintain the central database for the study.

Precision and accuracy of actual data collected will be checked by chart review (random 5%) and internal procedures using the computer program. Monthly audits and incomplete data reports will be performed by a review team consisting of at least of the SFI and the country coordinator. Data editing and error resolution will be performed monthly. In addition, a sample of participants will be visited to confirm their participation, with procedures determined per site. These activities will be shared between the site and the data center.

## **3.7 QUALITY CONTROL**

### **3.7.1 Training**

All study personnel must participate in training on the proper implementation of study procedures and the ethics of conducting research with human subjects before beginning any research activity. The SFI and project coordinator will ensure that all study personnel receive the appropriate training, and obtain the required certification ensuring that they have met the training objectives. RTI will be responsible for developing a certification test. The SFI and project manager will be responsible for overseeing the certification process.

### **3.7.2 Study Monitoring**

Major monitoring responsibilities of the PI/SFI, assisted by the country coordinator, are (1) confirming proper IRB approval; (2) monitoring the delivery of the study intervention; (3) assessing and evaluating the quality of study implementation; (4) ensuring compliance with the intervention, including proper randomization; (5) evaluating accuracy, precision, and completeness of data collected, entered, and transmitted (along with the DCC); (6) ensuring that all personnel are fulfilling their obligations; (7) maintaining morale and enthusiasm of the staff; (8) handling ad hoc problems and maintaining communication; (9) ensuring inter-site consistency; and (10) proposing improvements to the monitoring activities.

NICHD and the DCC staff will conduct site visits as needed. These visits will include review of individual participant records, including supporting data, to ensure protection of study participants, compliance with the protocol, and accuracy and completeness of records. The SFI/PI will make study documents (e.g., logbooks, data forms, staff training certificates) and pertinent hospital/clinic records readily available for inspection by the local IRB, site monitors, and the NICHD for confirmation of the study data.

### **3.7.3 Drug Quality Assurance and Monitoring**

The study drug manufacturer will have a Good Manufacturing Practices (GMP) designation vetted by the FDA and a certificate of authenticity will be provided. Each site will adapt best practice guidelines for drug shipment and storage to the needs and infrastructure of their local environment. Study staff will be trained in on the drug shipment and storage plan to ensure that best practices are maintained at all time. Additionally, participants will receive detailed instruction on proper storage of the study drug at home. Drug stability information will be maintained throughout the study. For quality assurance, a sample of pills from each site will be randomly selected and tested for bioavailability at multiple time points during the study period. A sample from each batch will be tested.

### **3.7.4 Ultrasound Gestational Age Dating**

All study sonographers will be trained to assess gestational age using CRL measurements. A sample of ultrasound images at each site will be reviewed by study investigators to ensure that CRL is accurately measured and gestational age is accurately assigned. If discrepancies are found, the sonographers will be retrained. Ultrasound will be used only for pregnancy dating and no other purpose.

## 4 DATA FORMS

The following forms will be used for this study:

Form Description	Purpose	Key Data Elements	Data Source
Screening Log	To track screening and enrollment at facility or community level	Contact information, screening and enrollment date and status	Patient report
Initial Screening and Recruitment	To determine eligibility and record consent status	Screening criteria: age, pregnancy history, estimated GA by LMP, consent status/date.	Patient report, obstetrical wheel,
Ultrasound Screening	To confirm eligibility criteria by ultrasound.	GA dating, assessment of fetal anomaly, singleton pregnancy, and fetal heart rate	Ultrasound
Hemoglobin (Hb) Monitoring	To monitor Hb at enrollment and 26-30 GA. It will also capture Hb at 4 weeks post-randomization in subset of 500 women	Hemoglobin	Lab test
Clinical Assessment	To assess clinical status through examination and patient history and provide information on medicine distribution/use	Height, weight, BP, Pulse, patient-reported medical history, use of other medications	Clinical exam, lab tests, patient report
Biweekly Monitoring	To monitor side effects, use of other medications, and drug compliance.	Drug compliance, BP, side effects (nausea, vomiting, rash/hives, diarrhea, vaginal bleeding, gastritis, other), use of other medicines, care seeking, pregnancy complications.	Pill count, patient report, clinical examination
Blood Pressure Monitoring	To monitor BP for active identification of pre-eclampsia	BP, urine protein (if indicated), fetal movement, diagnosis of eclampsia or stroke.	Clinical examination, patient report
Unscheduled Emergency Visit	To monitor unscheduled medical visits or medical emergencies	Patient status, pulse, BP, reason for medical visit/emergency, pill count and patient report on drug compliance, presence of side effects, referrals	Existing medical records, patient reports
Severe Adverse Events	To record fatal, life-threatening, or any other serious, unexpected adverse event	Date/time of event, date/time of resolution, nature of adverse event, management of adverse event, attribution to study (yes/no).	Patient reports, existing medical records
Study Withdrawal	To describe reasons for study termination or withdrawal	Date and reason for termination/withdrawal.	Patient report
Protocol Deviation	To record protocol deviations and corrective actions	Date and nature of deviation/violation, corrective action.	Patient report, study records
Outcomes	Maternal and Fetal outcomes will be documented via the GN's established MNH Registry	Preterm birth (primary outcome); maternal and fetal secondary outcomes.	MNH Registry

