# APPENDIX 1. SCHEDULE OF STUDY PROCEDURES

	6 0/7- 13 6/7 weeks GA	Randomization /Enrollment	Bi-weekly after enrollment	4 weeks after enrollment	monthly after enrollment	16-20 weeks GA	26-30 weeks GA	34 weeks GA	36 weeks GA until delivery	6 weeks Post-Partum	As needed
Screening											
• Initial eligibility	X										
• Ultrasound	X										
Consent	X										
Clinical Assessments											
• Physical exam		X									
• Medical history		X									
• Use of other medicines		X	X								
• Maternal Hb monitoring		X		X			X				
• BP Monitoring		X				X	X	X	X		
Medication Activities											
• Instructions for drug use		X									
• Medication compliance			X								
• Resupply					X						
Outcome Assessment											
• Preterm Birth										X	
• SGA										X	
• Preeclampsia/ Eclampsia			X							X	X
• Other maternal outcomes			X							X	X
• Other fetal outcomes										X	X
• Unanticipated medical care											X
• Serious Adverse Events											X

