Preeclampsia and eclampsia (or more appropriately hypertensive disorders of pregnancy)	Binary	
The unit of analysis is the woman randomized to the trial, but the outcome will be defined by the characterization of evidence of hypertensive disorder, including either preeclampsia or eclampsia occurring during the pregnancy. The algorithm for defining this endpoint is included as an addendum to this SAP in HypertensionAlgorithm_V1.1_10052018 (amendments to this algorithm may occur as part of the endpoint adjudication process and will be documented in new versions of this addendum accordingly).
 
 
• Briefly, any of the following will count as evidence of hypertensive disease: 
 
○ Any reported SAE of preeclampsia or eclampsia.
 
○ M NH registry report of hypertensive disease, preeclampsia or eclampsia.
 
○ Reports of elevated blood pressures that meet criteria based on the ACOG 2013 “Hypertension in Pregnancy” Task Force Report at any point after 20 weeks GA. 
 
▪ The only case that will programmatically qualify for evidence of hypertension is: Any individual with 2 consecutive timepoints with <math>\geq 140</math> mm Hg systolic or <math>\geq 90</math> mm Hg diastolic where those timepoints occur more than a week (7 days) apart. The criteria (e.g. elevated systolic or elevated diastolic) must be consistent for the two consecutive visits.
 
 
 
 
 
• For individuals that do meet the above criteria 
 
○ If they have less no reports of elevated blood pressure or a single report of elevated blood pressure that is followed by a normal value, they will not be considered to have evidence of hypertensive disease.
 
○ If they have any other reports of elevated blood pressure, their outcome classification will be adjudicated in a masked manner by clinical experts.
 
 
 
 
Will exclude any MTP but include withdrawals and terminations as data are available. Analysis Population: mITT
 
.

Variable	Type	Definition

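### As printed, SAP 9.2 gives the eclampsia diagnosis on the trial's own Blood Pressure Monitoring form no role in the hypertensive-disorder outcome

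*Combined protocol and SAP*

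**What the plan says.** **What is collected.** The form table in protocol section 4 gives the Blood Pressure Monitoring form the purpose "To monitor BP for active identification of pre-eclampsia" and lists its contents as "BP, urine protein (if indicated), fetal movement, diagnosis of eclampsia or stroke". The Biweekly Monitoring form ends its list with "use of other medicines, care seeking, pregnancy complications". The Unscheduled Emergency Visit form records blood pressure and the reason for the visit. Appendix 1 has an outcome-assessment row, "Preeclampsia/ Eclampsia", marked biweekly, at 6 weeks post-partum and as needed.

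**What counts.** SAP 3.2 defines the outcome as new hypertension beyond 20 weeks, preeclampsia or eclampsia, from the start of dosing to 6 weeks after delivery. SAP 9.2 then gives three routes to a case:

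- "Any reported SAE of preeclampsia or eclampsia";
- an MNH "registry report of hypertensive disease, preeclampsia or eclampsia";
- raised blood pressures after 20 weeks that meet the stated criteria. The only pattern accepted by program is two consecutive time points more than 7 days apart, both raised on the same component.

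**What happens to everyone else.** A woman with no raised reading is a non-case. So is one with a "single report of elevated blood pressure that is followed by a normal value, they will not be considered to have evidence of hypertensive disease". Only women with some other pattern of raised readings go to masked clinical adjudication. SAP 9.2 presents all this as a brief account of an algorithm held in a separate addendum.

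**The concern.** The rule takes blood pressure values recorded in the trial but, as printed, ignores the diagnosis on the form designed to monitor them. Case status for a recorded eclampsia then depends on whether an SAE form or registry entry was also completed. Eclampsia is the most severe component of this secondary outcome, so coding a recorded instance as absent is a validity problem even if it is rare.

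The same classification feeds the preterm preeclampsia outcome. SAP Table 5b also reports eclampsia by site, while SAP 9.2 gives eclampsia no derivation of its own.

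**Working it through.** **1. Trace one woman through the text.** Suppose eclampsia is recorded on the Blood Pressure Monitoring form, there is no SAE form and no registry entry, and she has either no raised reading or one raised reading followed by a normal one.

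| Step | Source | Result |
|---|---|---|
| Is she a case by definition? | SAP 3.2 | Yes, eclampsia within the window |
| SAE route | SAP 9.2 | Not met |
| Registry route | SAP 9.2 | Not met |
| Blood pressure route | SAP 9.2 | Not met |
| Sent to adjudication? | SAP 9.2 | No, this needs another raised-reading pattern |
| Final score | SAP 9.2 | Non-case |

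The last branch is printed as applying to women who *do meet* the criteria above it. It makes sense only as *do not meet*, and is read that way here.

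**2. Can readings substitute for the diagnosis?** Not reliably. Protocol Appendix 3 allows eclampsia to begin suddenly and to occur soon after delivery. The blood pressure row in Appendix 1 has no post-partum mark.

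**3. Does the SAE route close the gap?** Mostly. Protocol 3.5.1 requires the form for any event that is life-threatening or needs hospitalization, and eclampsia would normally qualify. The named triggers do not include it: "specific adverse events to be monitored in this trial include maternal death, upper GI bleeding (vomiting blood), fetal anomaly, gastroschisis, post-partum hemorrhage, or antepartum hemorrhage". Reporting therefore rests on the site applying the general criteria.

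**4. Reproduce the plan's power.** SAP 6.2 gives 5% risk, 5,483 evaluable per arm and a type I error of 0.05 (taken as two-sided). With d = p1 − p2 and p̄ the mean of p1 and p2:

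power = Φ[(d − 1.96·√(2p̄(1−p̄)/n)) / √((p1(1−p1) + p2(1−p2))/n)]

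For a 20% reduction, p1 = 0.05, p2 = 0.04 and n = 5,483. This gives (0.01 − 1.96 × 0.003959) / 0.003958 = 0.566, so power is 71.4%. For 24% and 26% reductions it is 86.5% and 91.6%. The plan states 70%, 85% and 90%, so its figures are reproduced to within 2 points.

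**5. Illustrate the loss.** The documents give no share of cases known only from trial forms. Let m be the assumed share of all cases missed, equal in both arms. Both risks are multiplied by (1 − m). Expected placebo cases are 0.05 × 5,483 = 274.

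| m | Placebo cases missed | Power, 20% reduction | Power, 24% | Power, 26% |
|---|---|---|---|---|
| 0 | 0 | 71.4% | 86.5% | 91.6% |
| 1% | 3 | 71.0% | 86.2% | 91.3% |
| 2% | 5 | 70.5% | 85.8% | 91.0% |
| 5% | 14 | 69.1% | 84.7% | 90.1% |
| 10% | 27 | 66.7% | 82.6% | 88.5% |

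Up to 2%, power stays above the plan's stated values; at 5% it is essentially equal to them. The 10% row is an outer bound without support in the documents: m applies to all hypertensive cases, whereas eclampsia, the only hypertensive disorder named as a diagnosis on these forms, is a subset of unstated size.

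**6. Relative risk.** With equal loss, the ratio is (1 − m)p2 / [(1 − m)p1] = p2/p1, which is unchanged.

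**The case against.** The strongest reply is that a miss needs several safeguards to fail together. The SAE form is mandatory for life-threatening events, and the named list in protocol 3.5.1 adds to the general criteria without limiting them. SAP Table 6 has a preeclampsia/eclampsia row, so the trial expects these events as SAEs. The registry is the designated source for outcomes (protocol section 4), and SAP section 12 ties this outcome to the registry's data collection. The emergency form also records blood pressure. All of this stands, and it is why the affected women should be few.

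The second reply is that SAP 9.2 is only a summary. The addendum was not available, may already use this field and may be amended during adjudication. SAP 7.6 also provides masked adjudication of selected secondary outcomes. This stands too, but the printed branches dispose of every woman, and SAP 7.6 does not mention diagnoses on forms. If the addendum differs, the SAP text should say so.

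A reader might infer that preeclampsia diagnoses in general are being discarded. The documents do not support that. The biweekly and emergency fields are generic, and preeclampsia requires hypertension by definition, so the blood pressure route or adjudication should reach much of it.

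**Conclusion.** The gap is real in the printed text: SAP 3.2 and SAP 9.2 classify the traced woman differently, and a diagnosis the trial already collects has no role. The expected size is small: under 1 point of power for a 20% reduction if 2% of cases are missed, and about 2 points if 5% are.

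These figures rest on an assumed, equal loss in both arms. It would be going too far to conclude that the treatment comparison is biased or the outcome underpowered: the trial is masked, equal loss leaves the relative risk unchanged, and SAP 7.5 treats secondary outcomes as exploratory. Nor can it be said that the final analysis will miscode such women, since the addendum may already prevent it. This is a cheap improvement to the outcome definition and does not threaten the trial's conclusions.

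**What to change.** In SAP 9.2 and, if not already there, in the algorithm addendum:

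- State that any eclampsia diagnosis on the Blood Pressure Monitoring form, and any explicit preeclampsia or eclampsia entry on the Biweekly Monitoring or Unscheduled Emergency Visit forms, sends the woman to the existing masked adjudication.
- State that the automatic no-evidence branch does not apply to her.
- Correct *do meet* to *do not meet* in that branch.

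The rule should not depend on whether a diagnosis came from examination or from the patient, because protocol section 4 gives data sources only for each form as a whole. The adjudicators can weigh the source.

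No new data are needed, adjudication already exists, and SAP 9.2 allows documented amendments to the algorithm. The change should be made before unmasking. The cost is a few more records to adjudicate, some of them patient-reported. If the addendum already covers this, only the SAP wording needs reconciling.
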